### 7.5.1. Prior Medication

Medications will be classified as prior if the medication stop date is before the treatment start date.

### 7.5.2. Concomitant Medication

Medications will be classified as concomitant if the medication start date is on or after the treatment start date, or if the medication start date is before the treatment start date and the medication stop date is on or after the treatment start date.

This document is confidential.

## 8. Clinical Efficacy

All summaries and analyses of clinical efficacy data will be based on observed data in the mITT Population. No imputation of missing data will be done and there will be no adjustments for multiplicity. Data from subjects who withdraw will be included, where possible, in all summaries and analyses.

### 8.1. RSV Clinical Scoring System Score

The RSV Clinical Scoring System gives a score from 0 to 12.

For each of Parts A, B and C, the RSV Clinical Scoring System score will be summarised at baseline and at each post-baseline time point. Summary statistics will be provided for the observed values and the corresponding changes from baseline for post-dose assessments. Plots of the mean  $\pm$  SD observed and change from baseline RSV Clinical Scoring System score by time point (baseline and each post-baseline assessment) will be presented. If necessary, lower SD bars will be truncated at 0 for the observed value plot.

For Part B, comparisons will be made between RV521 and placebo using a mixed effects analysis of covariance (ANCOVA) model on the change from baseline in RSV Clinical Scoring System score including a random effect term for subject, fixed effect terms for treatment group, age group ( $\geq 1$  month to  $< 6$  months or  $\geq 6$  months to  $\leq 36$  months at screening), visit and visit by treatment group interaction, and baseline RSV Clinical Scoring System score as a covariate. The model will be fitted to the 24 subjects treated at the final doses selected for Cohort 5 (see Section 6.1).

For Part C, comparisons will be made between RV521 and placebo using a mixed effects ANCOVA model on the change from baseline in RSV Clinical Scoring System score including a random effect term for subject, fixed effect terms for treatment group, visit, visit by treatment group interaction, duration of symptoms prior to randomisation and severity of illness at randomisation, and baseline RSV Clinical Scoring System score as a covariate.

For each model, a point estimate and 95% confidence interval will be calculated for the mean difference between RV521 and placebo.

Distributional assumptions underlying the statistical analyses will be assessed by visual inspection of residual plots. Normality will be examined by normal probability plots, while homogeneity of variance will be assessed by plotting the residuals against the predicted values for the model. If the distributional assumptions of a normal distribution in the parametric approach are not satisfied, investigations into influence of outliers or non-parametric methods will be considered.

In addition, for each of Parts A, B and C, the RSV Clinical Scoring System score will be categorised as:

- Mild – scores  $\leq 5$ .
- Moderate – scores  $> 5$  and  $< 9$ .
- Severe – scores  $\geq 9$ .

The number and percentage of subjects with mild, moderate and severe assessments will be summarised at baseline and at each post-baseline time point.

All tables for Part C, will also be presented by the subgroups defined in Section 6.6.

This document is confidential.

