## 6. General Aspects for Statistical Analysis

### 6.1. General Methods

- Unless otherwise specified, summaries for Part A will be presented by cohort, dose level and overall, summaries for Part B will be presented by cohort, treatment, dose level and overall, and summaries for Part C will be presented by treatment and overall.
- Unless otherwise specified, continuous variables will be summarised using the number of observations (n), mean, standard deviation (SD), median, minimum, and maximum. Means and medians will be presented with one more decimal than the observed values. SD values will be presented with 2 more decimals than the observed values.
- Unless otherwise stated, categorical variables will be summarised using number of observations (n), frequency and percentages of subjects.
- Presentations for PK data are described separately in Section 9. Presentations for PD data are described in Section 10.
- All relevant subject data will be included in listings. All subjects entered into the database will be included in subject data listings.
- All statistical testing will be 2-sided with an alpha level of 0.05, with no adjustment for multiple comparisons.
- For Part B, formal statistical testing will focus on the 24 subjects treated at the doses used in Cohort 5 that were identified in Cohorts 3 and 4. These 24 subjects comprise the whole of Cohort 5, plus the 4 subjects from each of Cohorts 3 and 4 that were randomized with the selected dose/placebo.
- Where there are multiple assessments at a given time point, only the results recorded on the scheduled time point page of the case report form (CRF) will be used for summarisation, unscheduled assessments will be listed only.

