## 8.2. Adapted Version of ReSVinet Scale for Parental Use

The Adapted Version of ReSVinet Scale for Parental Use is used in study Parts B and C and gives a score from 0 to 20.

For Parts B and C, the continuous Adapted Version of ReSVinet Scale for Parental Use scores will be summarised and analysed as for the RSV Clinical Scoring System scores.

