## 15. Changes from Version 1.0 of the SAP

The following updates from Version 1.0 of the SAP, dated 09-Oct-2020 have been made:

- Update to definition of MITT population for Parts B and C to take into account the possibility that we may have subjects who do not ingest the administered doses but who do not withdraw from the study. The following has been added to the definition of the MITT population: 'Inclusion of subjects who have not completed at least 6 doses of IMP will be agreed by the project team during blind data review.'
- For Part B, it is clarified that formal statistical analyses will focus on the 24 subjects treated at the final doses selected for Cohort 5.
- To allow for a different treatment effect to be estimated at each visit, for the RSV Clinical Scoring System and the Adapted Version of ReSVinet Scale for Parental Use, the mixed model analyses will also include fixed effect terms for visit and visit by treatment group interaction. Furthermore, for Part B, as the analyses will focus on the 24 subjects treated at the final doses selected for Cohort 5, dose is no longer required to be fitted to the model as a fixed effect as this is now synonymous with age group.
- For the formal statistical analyses of the PD data for Part B, as the analyses will focus on the 24 subjects treated at the final doses selected for Cohort 5, dose is no longer required to be fitted to the model as a fixed effect as this is now synonymous with age group. In addition, analyses will be repeated with the addition of an interaction term to the model for treatment group by presence or absence of other known respiratory pathogens. This will enable the treatment effect given the presence or absence of the pathogens to be investigated.

This document is confidential.

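### SAP 8.1 fits the repeated clinical scores with only a random subject effect and one baseline slope, which implies equal variance at every visit, so visit-specific intervals are likely miscalibrated

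*SAP*

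**What the plan says.** SAP 8.1 fits a mixed "model on the change from baseline in RSV Clinical Scoring System score". For Part C the model is specified as "including a random effect term for subject, fixed effect terms for treatment group, visit, visit by treatment group interaction", plus the two stratification factors "and baseline RSV Clinical Scoring System score as a covariate". It names no residual covariance structure and no baseline-by-visit term. Part B uses the same form with age group, fitted to 24 subjects.

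SAP 15 gives the reason for the visit terms: "To allow for a different treatment effect to be estimated at each visit". Protocol 11.1.5 likewise plans to compare arms on the composite score day by day in hospital and at follow-up.

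The planned check is that "homogeneity of variance will be assessed by plotting the residuals against the predicted values for the model". If normality fails, "investigations into influence of outliers or non-parametric methods will be considered". No other covariance structure is offered.

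SAP 8.2 says the parental ReSVinet scores "will be summarised and analysed as for the RSV Clinical Scoring System scores". SAP 6.1 sets the error rate: "All statistical testing will be 2-sided with an alpha level of 0.05, with no adjustment for multiple comparisons".

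**The concern.** A single random subject effect with default residuals estimates one total variance and applies it to every visit. If the true residual variance differs by visit, the standard error is too small where the spread is large and too large where it is small. A common baseline slope adds to this, because the relation between change and baseline shifts as infants recover.

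The modelled score runs from 0 to 12 and cannot fall below 0. SAP Table 3 schedules it from the day after first dosing to Day 28, a span over which most infants should move from ill to well. Constant spread is unlikely over that course.

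The per-visit comparison of severity is at stake. SAP 4.4 lists the composite score among the Part C primary endpoints; Protocol 7.2 lists it as secondary. With no covariance alternative written down, any repair would have to be chosen after the data are seen.

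**Working it through.** The documents give no SD, standard error or power for this score, so there is no planned figure to reproduce. The check has two steps.

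**Step 1. How far a pooled variance can mislead.** Let v_t be the residual variance at visit t and n the number per arm. With complete data:

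- Model SE at every visit ≈ √(2 × mean(v) / n)
- True SE at visit t = √(2 × v_t / n)
- Ratio = √(mean(v) / v_t), so n cancels
- Coverage = 2Φ(1.96 × ratio) − 1

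The residual variance under a common slope b is v_t = Var(change_t) − 2b·Cov(change_t, baseline) + b²·Var(baseline).

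The post-baseline visits follow SAP Table 3: Days 2, 3, 4, 5, 7, 14 and 28. All SDs and correlations with baseline are assumptions:

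- A: baseline SD 2; score SDs 1.9, 1.8, 1.7, 1.5, 1.2, 0.6, 0.3; correlations 0.6, 0.5, 0.4, 0.35, 0.3, 0.1, 0.05.
- B: SDs as in A; correlations 0.9, 0.8, 0.7, 0.6, 0.4, 0.1, 0.05.
- C: baseline SD 1.5; score SDs 1.6, 1.8, 2.0, 2.0, 1.8, 1.0, 0.5; correlations 0.9, 0.75, 0.6, 0.5, 0.35, 0.15, 0.05.
- D: all SDs 2; correlations 0.9, 0.8, 0.7, 0.6, 0.45, 0.2, 0.1.
- E: all SDs 2; all correlations 0.5.

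Scenario A, worked through: residual SDs are 1.64, 1.60, 1.57, 1.41, 1.16, 0.76, 0.59. Their squares sum to 11.97, so mean(v) = 11.97/7 = 1.71 and its root is 1.31. The Day 2 ratio is 1.31/1.64 = 0.80, giving coverage 2Φ(1.57) − 1 = 88%. The Day 28 ratio is 1.31/0.59 = 2.2, giving coverage of about 100%.

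Ratio of model SE to true SE (below 1 means the interval is too narrow):

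| Scenario | D2 | D3 | D4 | D5 | D7 | D14 | D28 |
|---|---|---|---|---|---|---|---|
| A | 0.80 | 0.81 | 0.83 | 0.93 | 1.13 | 1.73 | 2.21 |
| B | 0.94 | 0.92 | 0.90 | 0.95 | 0.99 | 1.17 | 1.31 |
| C | 1.50 | 1.07 | 0.85 | 0.80 | 0.82 | 1.16 | 1.47 |
| D | 1.49 | 1.29 | 1.15 | 1.05 | 0.94 | 0.82 | 0.78 |
| E | 1.00 | 1.00 | 1.00 | 1.00 | 1.00 | 1.00 | 1.00 |

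In D the pattern is the reverse of A: coverage is 99.6% at Day 2 and 87% at Day 28. A simulation of A to D (4,000 trials each, 37 per arm) agreed with these ratios within 0.04.

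**Step 2. Which patterns fit the SAP's own planning figures.** SAP 3.7 assumes a median of 15 days to absence of all symptoms and an interquartile range of 9 days. The upper quartile is then 15 + 4.5 = 19.5 days if symmetric, and at most 15 + 9 = 24 days. At least three quarters are symptom-free before Day 28, which makes the constant spread of D implausible.

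Bounded 0–12 scores were simulated with no treatment effect: upper quartile 19.5 or 24 days, three decline shapes and two noise levels (2 × 3 × 2 = 12 scenarios), 37 per arm, 2,000 trials each. Baseline mean 7 (SD 2), noise and shapes are assumptions.

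- Last visit: model SE 1.3–2.5 times the true SE; false-positive rate 0–1.4%.
- Worst earlier visit: false-positive rate 8–11% in all 12 scenarios.
- Fast early decline puts the excess on Days 2–5. Linear decline moves it to Days 7–14 and leaves Day 2 correct or too wide.

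A separate simulation on the same basis gave about 9–11% and 0–1.5%. Visit-specific variances brought the rate back to about 5%, except at Day 28, where near-zero scores made it erratic.

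Limits: the step 1 calculation takes scores as normal with complete data. It does not model the footnote to SAP Table 3 that restricts the score to hospitalised subjects.

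**The case against.** The strongest reply is that direction cannot be known. The response is change from baseline, so early change may vary little if early scores track baseline. Scenarios C and D show intervals too wide at Day 2. This stands. A reader might infer that early intervals are always too narrow and late ones always too wide; the documents do not support that as fact.

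Nor do they support a larger size. If the residual SD is taken to fall from 2.5 to 0.3, the early false-positive rate reaches 13–16% and late standard errors are 2.3–6 times too large. A late SD of 0.3 is hard to defend. Protocol Appendix 17.1 scores respiratory rate without regard to age, giving 1 point for 31–45 and 2 for 46–60. Appendix 17.6 lists 40–50 as normal below 2 months and 35–45 at 2–6 months. A recovered young infant can still score 1 or 2, so some late spread remains. The common slope also leaves residual variance at late visits.

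It would also be too strong to say that the SAP forces equal variance. It is silent on residual structure, and equal variance is the default reading. It does plan a residual plot, but the remedy is tied to normality and names no covariance alternative.

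On scope, Day 34 does not belong to the score SAP 8.1 models. The SAP's Part C ends at Day 28 and Part B scoring at Visit Day 7. Day 34 is in the Protocol, which in Part C collects a different clinician score (ReSVinet, 0–20). For the parental scale, the SAP schedules one post-baseline visit, so pooling across visits cannot arise. It does arise under Protocol Table 3a, which schedules several.

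Finally, SAP 8.1 promises one mean difference per model. The visit-averaged comparison is adequately calibrated with complete data (5.6% in a check). That protects the average, not the per-visit effects that SAP 15 says the model is meant to give.

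**Conclusion.** The point holds in limited form. As written, SAP 8.1 implies one variance and one correlation across visits for a bounded recovery score whose per-visit effects are meant to be read, and it names no alternative. Under recovery curves consistent with the SAP's 15-day median, expect a false-positive rate of about 9–11% at the worst earlier visit and about 0–1.5% at the last, against a nominal 5%. Late over-width appears in every bounded scenario; which earlier visit is too narrow depends on the shape of decline. These figures rest on assumed baseline, noise and shape, because no spread by visit is given.

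The consequence is confined to the clinical-score analyses. The Protocol's Part C primary endpoint, time-weighted average change in viral load, has one value per subject and is untouched. The change is worth making because it is cheap and the alternative is clearly better.

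**What to change.** **Part C.** Replace the random-intercept model with a repeated-measures model with unstructured within-subject covariance, a baseline-by-visit term and Kenward-Roger degrees of freedom. Pre-specify the order of fallback if it does not converge: heterogeneous Toeplitz, then heterogeneous compound symmetry. State that if almost all scores are 0 at the last visit, that visit is summarised descriptively, and write the threshold down before unblinding. Apply the same model to the parental scale if the Protocol's multi-visit schedule is the one followed.

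**Part B (24 subjects, 16:8).** Use a heterogeneous-variance structure with Kenward-Roger. Use robust standard errors only with a small-sample correction. In a check with 4,000 null trials, five visits, assumed SD falling from 2.5 to 1.0 and correlation 0.7, uncorrected robust errors gave 8–10% false positives per visit, and 6.5–8% with t critical values.

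**Cost.** A few lines of SAP text. Protocol 11.1 allows SAP amendments for Parts B and C before database lock and unblinding of the part concerned, and the Part C score and schedule have to be aligned with the Protocol anyway. The price is more covariance parameters (7 × 8 / 2 = 28 for seven visits, against 2 now) and a small risk of non-convergence, which the fallback covers.

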## 8.2. Adapted Version of ReSVinet Scale for Parental Use

The Adapted Version of ReSVinet Scale for Parental Use is used in study Parts B and C and gives a score from 0 to 20.

For Parts B and C, the continuous Adapted Version of ReSVinet Scale for Parental Use scores will be summarised and analysed as for the RSV Clinical Scoring System scores.

## 8.3. RSV-related Signs and Symptoms

RSV-related signs and symptoms (temperature, respiratory rate, coryza, cough, grunting with expiration, nasal flaring, retractions, wheezing and SpO2 on Room air) will be collected on the CRF at each time point identified in the Schedule of Assessments for Part B (Table 2), and Part C (Table 3) in Section 3.10.

For study Parts B and C, assessments of individual RSV-related signs and symptoms will be summarised at each time point. For quantitative variables, observed values and changes from baseline will be summarised. In addition, highest level of severity during the study for each individual RSV-related sign and symptom will be summarised using summary statistics for categorical variables.

Time to improvement will be calculated for RSV-related signs and symptoms that are classified as moderate or severe during the course of the study and will be defined as the time from randomisation until no longer present (absent or severity=0) or mild. If there is no improvement, then time to improvement will be censored as the date/time RSV-related signs and symptoms were last recorded. Time to improvement will be summarised (number [%] of subjects analysed, mean, median, SD, minimum, maximum) for Parts B and C. The overall time to improvement will be defined as the time from randomisation to the time that all RSV-related signs and symptoms are mild or absent. The overall time to improvement will be summarised for Parts B and C by n, mean, median, SD, minimum, maximum and 95% confidence intervals for the mean. For Part C only, time to improvement of symptoms and overall time to improvement, will be compared between RV521 and Placebo using a Generalised Wilcoxon analysis, which is a weighted log-rank test, weighted by the number of subjects at risk immediately prior to the event, and will include duration of symptoms prior to randomisation as a covariate. Also for Part C only, Kaplan-Meier plots for time to improvement of symptoms and overall time to improvement will be presented by treatment.

Time to resolution will be calculated for RSV-related signs and symptoms that are present at study start and will be defined as the time from randomisation until no longer present (absent or severity=0). If there is no resolution, then time to resolution will be censored as the date/time RSV-related signs and symptoms were last recorded. The overall time to resolution will be defined as the time from randomisation to the time that all RSV-related signs and symptoms are no longer present (absent or severity=0). The time to resolution and the overall time to resolution will be summarised and analysed as for time to improvement.

Times to improvement or resolution will be presented in days to 1 decimal place.

All tables for Part C, will also be presented by the subgroups defined in Section 6.6.

## 8.4. Supplemental Oxygen Use

The number and percentage of subjects with supplemental oxygen use will be presented overall, at baseline and at each post-baseline time point. Reason for use of supplemental oxygen use will also be summarised.

This document is confidential.

Duration of use and overall maximum flow rate of oxygen will be summarised using summary statistics for continuous data. Duration of supplemental oxygen use will be calculated in hours from the start time of first use in the study to the end time of the last use in the study, i.e. ignoring any interruptions, and presented to 1 decimal place.

All tables for Part C, will also be presented by the subgroups defined in Section 6.6.

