7.2 PART C: Objectives and Endpoints

Primary Objectives for Part C	Primary Endpoint

 • Evaluate the antiviral effects of RV521, compared to placebo, on nasopharyngeal shedding of RSV in infants hospitalised with RSV LRTI 	
 • Time-weighted average change from Baseline to Day 7 in RSV viral load measured in nasopharyngeal swabs by RT-qPCR.
Secondary Objectives for Part C	Secondary Endpoints

 • To evaluate virologic parameters derived from the RSV viral load as measured in nasopharyngeal swabs • CCI [REDACTED] 	
 • Virologic parameters derived from the RSV viral load as measured in nasal swabs include but are not limited to: 
 ○ Change from baseline in viral load (RT-qPCR and CBIA) at each time point ○ Time to below viral load quantification limit (RT-qPCR and CBIA) ○ Proportion of subjects with viral load below quantification limit (RT-qPCR and CBIA) at each timepoint throughout the study • CCI [REDACTED]

 To evaluate the clinical efficacy of multiple oral doses of RV521 in infants hospitalised with RSV LRTI Evaluate the safety and tolerability of RV521 given as a multiple dose regimen 	
 Time to resolution in RSV-related symptoms Time to improvement of RSV-related symptoms Reduction in severity of symptoms by RV521, compared to placebo, measured by a composite score over time Use of supplementary oxygen, including, but not limited to, duration and maximum level of O₂ provided Time to normalisation of respiratory rate Safety of RV521 compared to placebo assessed by incidences of AEs, discontinuations due to AEs, SAEs, and clinically significant changes in laboratory tests

Exploratory Endpoints (Part C)
	
 [REDACTED] [REDACTED] [REDACTED]

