9.3 Treatment Period Part B

9.3.1 Dosing Visit 1 (Part B)

-2 Hours to 0 Hours Pre-Dose 1:

- Reassess for eligibility against the inclusion and exclusion criteria
- Physical examination (symptom-directed examination, general condition, lung auscultation, and respiratory muscles retractions)
- Evaluation of hydration status
- Vital signs (body temperature, systolic and diastolic BP, HR, RR)
- Record the use of supplemental oxygen, method of delivery (eg, nasal cannula), percent O₂/flow rate supplied
- Pulse oximetry on room air (if deemed safe by PI or health care provider)
- RSV Clinical Scoring System ([Appendix 17.1](#))
- Record RSV-related signs and symptoms and severity every 12 hours (if indicated), including: temperature, cough, coryza, grunting with expiration, nasal flaring, retractions, and wheezing.
- Nasopharyngeal swab according to sampling schedule in Table 4
- Concomitant medication review
- Adverse event review
- Randomisation for eligible subjects

Note: If any of the assessments above were carried out within 2h Pre-Dose 1 for screening purposes, it is not necessary to repeat that assessment for the -2h to 0h Pre-Dose 1 timepoint. However, if the assessment was carried out >2 h prior to Dose 1 for screening purposes (i.e. within the first 22 hours of the screening window), the assessment must be repeated between -2h to 0h Pre-Dose 1.

Dosing (0 Hours):

- Vital signs (body temperature, systolic and diastolic BP, HR, RR)
- Study medication administration
- The times of the prior feeding and first feeding after dosing should be recorded.
- Adverse event review
- Concomitant medication review

1-2 Hours or 4-5 Hours or 6-8 Hours Post-Dose 1:

The following assessments will be carried out at either 1 to 2 hours, 4 to 5 hours or 6 to 8 hours Post-Dose 1. The time point chosen (1-2, 4-5 or 6-8 hours) will be defined after PK analysis of Part A.

- Vital signs (body temperature, systolic and diastolic BP, HR, RR)
- 12-Lead ECG
- PK blood sample according to sampling schedule in [Table 5](#)
- Concomitant medication review
- Adverse event review

12 Hours Post-Dose 1 (Pre-Dose 2):

- Vital signs (body temperature, systolic and diastolic BP, HR, RR)
- Pulse oximetry on room air (if deemed safe by PI or health care provider)
- Record the use of supplemental oxygen, method of delivery (eg, nasal cannula), percent O₂/flow rate supplied

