9.4.1 Dosing Visit 1 (Part C)

-2 Hours to 0 Hours Pre-Dose 1:

- Reassess for eligibility against the inclusion and exclusion criteria
- Physical examination
- Evaluation of hydration status
- Vital signs (body temperature, systolic and diastolic BP, HR, RR)
- ReSVinet Scale for Clinicians ([Appendix 17.6](#))
- Record RSV-related signs and symptoms, and severity every 12 hours (if indicated), including: temperature, cough, coryza, grunting with expiration, nasal flaring, retractions, and wheezing

- Record the use of supplemental oxygen, method of delivery (eg, nasal cannula), Percent O₂/Flow rate supplied
- Pulse oximetry on room air (if deemed safe by PI or health care provider)
- Randomisation for Eligible Subjects (stratified by age group)
- Nasopharyngeal swab
- Concomitant medication review
- Adverse Events

Note: If any of the assessments above were carried out within 2 h Pre-Dose 1 for screening purposes, it is not necessary to repeat that assessment for the -2 h to 0 h Pre-Dose 1 timepoint. However, if the assessment was carried out >2 h prior to Dose 1 for screening purposes (i.e. within the first 22 hours of the screening window), the assessment must be repeated between -2 h to 0 h Pre-Dose 1.

Dosing (0 Hours):

- Concomitant medication review
- Adverse event review
- Study medication administration (Dose 1)
 - The times of the prior feeding and first feeding after dosing should be recorded.

+4-5 Hours Post-Dose 1:

The following assessments will be carried out at 4 to 5 hours Post-Dose 1.

- Vital signs (body temperature, systolic and diastolic BP, HR, RR)
- 12-Lead ECG
- Concomitant medication review
- Adverse event review
- PK blood sample according to sampling schedule in [Table 5](#). **Note:** This sample will only be required if the dose level was not previously evaluated in Part B.

12 Hours Post-Dose 1 (Pre-Dose 2):

- Vital signs (body temperature, systolic and diastolic BP, HR, RR)
- Record RSV-related signs and symptoms, and severity every 12 hours (if indicated), including: temperature, cough, coryza, grunting with expiration, nasal flaring, retractions, and wheezing
- Record the use of supplemental oxygen, method of delivery (eg, nasal cannula), Percent O₂/Flow rate supplied
- Pulse oximetry on room air (if deemed safe by PI or health care provider)
- Optional Nasopharyngeal swab according to sampling schedule in [Table 4](#)
- Concomitant medication review
- Adverse event review

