17.6 ReSVinet Scale for Clinicians

Item	0 points	1 points	2 points	3 points
1 Feeding intolerance	No	Mild Decreased appetite and/or isolated vomits with cough.	Partial Frequent vomits with cough, rejected feed but able to tolerate fluids sufficiently to ensure hydration.	Total Oral intolerance or absolute rejection of oral feed, not able to guarantee adequate hydration orally. Required nasogastric and/or intravenous fluids
2 Medical intervention	No	Basic Nasal secretions aspiration, physical examination, trial of nebulized bronchodilators, antipyretics.	Intermediate Oxygen therapy required. Complementary exams were needed (chest X-rays, blood gases, hematimetry...). Maintained nebulized therapy with bronchodilators.	High Required respiratory support with positive pressure (either non-invasive in CPAP, BiPAP or high-flow O ₂ ; or invasive through endotracheal tube).
3 Respiratory difficulty	No	Mild Not in basal situation but does not appear severe. Wheezing only audible with stethoscope, good air entrance. If modified Wood Downes, Wang score or any other respiratory distress score is applied, it indicates mild severity.	Moderate Makes some extra respiratory effort (intercostal and/or tracheosternal retraction). Presented expiratory wheezing audible even without stethoscope, and air entrance may be decreased in localized areas. If modified Wood Downes, Wang score or any other respiratory distress score is applied, it indicates moderate severity.	Severe Respiratory effort is obvious. Inspiratory and expiratory wheezing and/or clearly decreased air entry. If modified Wood Downes, Wang score or any other respiratory distress score is applied, it indicates high severity.
4 Respiratory frequency	Normal < 2 m: 40–50 bpm 2–6 m: 35–45 bpm 6–12m: 30–40 bpm 12–24m:25–35 bpm 24–36m: 20–30 bpm	Mild or occasional tachypnea Presented episodes of tachypnea, well tolerated, limited in time by self-resolution or response to secretion aspiration or nebulization.	Prolonged or recurrent tachypnea Tachypnea persisted or recurred despite secretion aspiration and/or nebulization with bronchodilators.	Severe alteration Severe and sustained tachypnea. Very superficial and quick breath rate. Normal/low breath rate with obvious increased respiratory effort and/or mental status affected. Orientative rates of severe tachypnea: < 2 m: > 70 bpm 2–6 m: > 60 bpm 6–12m: >55 bpm 12–24m: >50 bpm 24–36m: >40 bpm

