##### Primary Endpoints for Part C

- Time to resolution of symptoms
- Time to improvement of symptoms
- Reduction in severity of symptoms by RV521, compared to placebo, measured by a composite score over time
- Use of supplemental oxygen, including, but not limited to, duration and maximum level of oxygen provided

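### SAP 8.4 measures maximum oxygen level by flow rate alone, so support recorded only as a percentage gives no value and flows from different devices are pooled

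*SAP*

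**What the plan says.** Protocol 7.2 lists the Part C secondary endpoint as "Use of supplementary oxygen, including, but not limited to, duration and maximum level of O₂ provided". SAP 4.4 has nearly the same words among its Part C primary endpoints: "Use of supplemental oxygen, including, but not limited to, duration and maximum level of oxygen provided". The two documents rank the endpoint differently, but both define it by level of oxygen. The planned SAP tables for Parts A, B and C also carry maximum level in their titles.

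Protocol 9.4.1 tells Part C sites to "Record the use of supplemental oxygen, method of delivery (eg, nasal cannula), Percent O₂/Flow rate supplied". Section 9.3.1 has the same instruction for Part B.

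The only derivation is in SAP 8.4: "Duration of use and overall maximum flow rate of oxygen will be summarised using summary statistics for continuous data". That section also reports the number and percentage of infants on oxygen overall and at each time point, the reason for use, and how duration is calculated. It does not mention delivery method or percent oxygen. It does not say how high-flow, CPAP or ventilation is to be handled, or whether an infant never on oxygen enters the flow summary. SAP section 8 as a whole uses observed data without imputation.

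**The concern.** Level of oxygen and rate of flow are different quantities. Sites are asked for three items (method, percent, flow) and the derivation keeps one. A record with a percentage and no flow cannot contribute to a maximum flow, and with no imputation nothing replaces it. A flow figure is also hard to interpret without the device: litres per minute through a low-flow cannula and through a high-flow or pressure system do not describe the same degree of support.

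The infants most exposed are those whose support was stepped up, which are the ones a maximum-level endpoint is meant to pick out. The plan foresees them. Protocol 8.4.4 lists a need for mechanical ventilation, positive airway pressure or high-flow oxygen as a reason a subject may be withdrawn. The ReSVinet clinician scale (Protocol 17.6) has a top medical-intervention grade for "Required respiratory support with positive pressure", which includes CPAP, BiPAP, high-flow oxygen and endotracheal support. What is at stake is whether the table headed maximum level describes how much support infants needed.

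**Working it through.** The plan states no figure for this endpoint, so the check is to apply the SAP rule to example records.

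**Rule.** For infant i with oxygen records j, M_i = max over j of F_ij, taken over records where flow F_ij is present. If no flow is present, M_i is missing.

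**Example records (assumed; the case report form is not in the documents).**

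| Infant | Records | M_i under SAP 8.4 | Highest support type |
|---|---|---|---|
| A | cannula 2 L/min, then CPAP at 40% with no flow entered | max(2) = 2 L/min | positive pressure or high-flow |
| B | cannula 2 L/min throughout | max(2) = 2 L/min | oxygen therapy |
| C | CPAP at 40% only, no flow entered | missing | positive pressure or high-flow |

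A and B receive the same value although A was stepped up. C is absent from the maximum-level summary. All three count in n (%) with oxygen use and in duration.

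**If flow is always entered.** Take 34 infants, 30 on cannula at 0.5 L/min and 4 on high-flow at 10 L/min (assumed values).

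- Sum: 30 × 0.5 + 4 × 10 = 15 + 40 = 55
- Mean: 55/34 = 1.62 L/min
- Share of the sum from the 4 high-flow infants: 40/55 = 73%
- Median 0.5 L/min; maximum 10 L/min

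No value is missing here, but the mean of 1.62 L/min describes neither group. By support type the same data read 30/34 (88%) oxygen therapy and 4/34 (12%) positive pressure or high-flow.

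**How many infants.** The documents give no escalation rate. With the planned 37 per arm and assumed rates:

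- 5%: 37 × 0.05 = 1.85, about 2
- 10%: 37 × 0.10 = 3.7, about 4
- 20%: 37 × 0.20 = 7.4, about 7

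At each assumed rate this counts all escalated infants. Those whose escalated support was recorded without a flow value would be some part of that number, and the documents do not say what part.

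**Is the level of support reported elsewhere in the SAP?** SAP 8.1 analyses the RSV Clinical Scoring System, whose items (respiratory rate, wheezing, retraction, general condition) do not include support. SAP 8.2 analyses the parental ReSVinet as a total score. The ReSVinet clinician scale does not appear in SAP section 8, and Protocol 11.1.5 summarises it as a score. Its middle intervention grade also covers chest X-rays, blood gases and maintained nebulised treatment, so even that item would not isolate oxygen.

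**The case against.** The strongest reply is that the slash between percent and flow may mean both fields are completed. The case report form is unseen, and the SAP's choice of flow suggests its authors expected a flow value. This stands: a percentage standing in place of flow is one reading, not an established fact. It removes the missing-value problem if both fields are always filled, but not the pooling of flows across devices.

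Three stronger readings are tempting, and the documents do not support them.

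- A reader might infer that escalated infants disappear from the oxygen outcome. They do not. SAP 8.4 still counts them in use and duration, the oxygen listing covers all subjects, and SAP 7.1 tabulates reasons for withdrawal. Only the maximum-level summary can lose them.
- A reader might infer that the comparison between arms would point the wrong way, or that a few high-flow infants would hide behind a mean. SAP 8.4 plans no test, and nothing in the documents shows a direction. SAP 6.1 also reports the median, minimum and maximum, so skew of the kind in the example would be visible.
- A reader might infer that a fine ordering of devices with a proportional-odds analysis is needed. The ReSVinet clinician scale puts high-flow, CPAP, BiPAP and invasive support in one grade, and a formal test would add inference to a component planned as descriptive.

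The lack of adjustment of flow for body weight carries little weight here. Allocation is randomised and stratified by age, so it adds noise rather than an expected difference between arms.

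**Conclusion.** The point holds. The stated derivation, maximum flow, does not measure the stated endpoint, maximum level of oxygen. Two consequences follow. Records held only as a percentage contribute nothing, so an escalated infant can keep a cannula value or be missing from this one summary; this depends on how the form was completed. Flows from devices that are not comparable are pooled, and this remains even with complete flow data.

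The effect is confined to one descriptive component of the oxygen endpoint. No sample size, power, p-value or type I error changes. The number of infants involved cannot be taken from the documents; about 2 to 7 of 37 per arm corresponds to assumed escalation rates of 5% to 20%. It is worth correcting because the table would carry the name of an endpoint that it does not report.

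**What to change.** In SAP 8.4, define maximum level as the highest support category after the first dose, derived from the recorded delivery method. Use the grouping already in the ReSVinet clinician scale: none; oxygen therapy; positive pressure or high-flow, including invasive support. Count infants never on oxygen as none, and report n (%) by arm. Show maximum flow rate and maximum percent oxygen descriptively within each delivery method. No formal test or finer ordering is required.

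The cost is one derived variable and one more table, from items the protocol already asks sites to record. The team should confirm that the delivery-method options on the case report form allow the three groups to be separated. The timing is convenient: SAP version 2.0 still describes Part C as 1:1 with about 120 subjects, against 1:1:1 and 111 in the protocol, so its Part C text needs revision anyway. Protocol 11.1 allows SAP amendments before database lock and unblinding of the part concerned.
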